5.3.3. Intention-to-Treat Population

The intention to treat (ITT) population shall consist of all enrolled subjects regardless of whether they received lenalidomide. The ITT population will be used for the analysis of all efficacy-based endpoints and for listings if not otherwise specified.

5.3.4. Safety population

The safety population consists of all subjects receiving at least one dose of lenalidomide and shall be applied to all safety based endpoints.

5.3.5. Pharmacokinetic Population

The PK population consists of all subjects receiving at least one dose of lenalidomide and having at least one measurable lenalidomide concentration. The PK population shall be used for analysis of PK data.

[REDACTED]

6. SUBJECT DISPOSITION

Subject disposition (analysis population allocation, entered, discontinued, along with primary reason for discontinuation) will be summarized using frequency counts and percent for each phase of the study.

Subjects completing the Screening Phase and reasons for screen failures, as collected in the eCRF page “Disposition - Screening” will be presented for all screened subjects (defined as subjects having a signed ICF/IAF) using the following categories:

- Completed
- Screen failure
- Death
- Adverse Event
- Withdrawal by subject
- Lost to follow-up
- Withdrawal by parent/guardian
- Other
- Missing

Completed subjects and reasons for treatment discontinuation during the fixed Treatment Phase as recorded in the “Disposition - Treatment” eCRF page will be summarized for intention to treat subjects with the following categories:

- Completed
- Death
- Adverse event
- Withdrawal by subject
- Lost to follow-up
- Withdrawal by parent/guardian
- Pregnancy
- Non-compliance with study drug
- Physician decision
- Protocol violation
- Other
- Missing

Subjects completing the study OEP/Follow-up Phase and reasons for not completing it will be collected on the eCRF (“Disposition - Treatment OEP” or “Disposition - Follow-up” pages) and will be summarized for all intention to treat subjects with the following categories in two separate tables:

- Completed
- Death
- Adverse event*
- Withdrawal by subject
- Lost to follow-up
- Withdrawal by parent/guardian
- Pregnancy*
- Non-compliance with study drug*
- Physician decision*
- Protocol violation*
- Other
- Missing

*Not applicable to the Follow-up Phase.

Table for the OEP phase will report disposition only for subjects who will have entered the OEP treatment period.

Analysis population allocation will be tabulated and listed. A summary of subjects enrolled by site will be provided.

Listings will be provided about patient disposition for all periods after the treatment start (first 12 cycles, optional extension phase, follow-up), for subjects who failed eligibility criteria and for subjects with previous participation to the study screening.

7. PROTOCOL DEVIATIONS/VIOLATIONS

The protocol deviations/violations will be identified and assessed by the clinical monitor of the sponsor or designee following company standard operational procedure: these possible deviations and violations are entered into the clinical trial management system by the clinical monitor and are reviewed by the sponsor for confirmation/correction. This adjudicated file will be used for analysis.

The protocol violations will be summarized for the ITT population using frequency tabulations. Moreover frequencies will be provided for number of subject with one, two or more than two protocol violations.

A listing of subjects with protocol violations/deviations in the ITT population will be provided.

8. BACKGROUND AND DEMOGRAPHIC CHARACTERISTICS

The demographics and baseline characteristics will be summarized in the ITT population. Individual subject listings will be provided to support the summary tables.

8.1.1. Demographics

The following demographics will be summarized descriptively:

- Age (years)
- Sex
- Race
- Ethnicity
- Reproductive Status
- Weight (kg)
- Height (cm)

For age, also frequency counts and percentages for the following categories will be presented: \leq 2, 3-6, 7-12, 13-16, 17-18 years. Years reached are to be used for categorization.

During calculation of age, when day of birth is missing (e.g. for regulatory authority directions) impute first day of the month, as requested in Section 18.3.1. Both ages, computed and collected in the eCRF, will be summarized.

Listing will be provided for demographic characteristic. Within listings, age will be displayed in years and months as computed following directions given in Section 18.3.1 while within tables summary statistics for age in years will be used.

8.1.2. Baseline Characteristics

The following baseline clinical characteristics will be summarized descriptively:

- Lansky and Karnofsky performance score (for subjects \leq 16 and $>$ 16 years of age, respectively)
- Baseline electrocardiogram (ECG)
- Vital Signs (with respiratory rate)
- White blood cell count
- Absolute blasts
- Absolute neutrophils
- Platelets
- Peripheral blood smear blasts
- Bone marrow differential

8.1.3. Medical History

All medical history, up to 5 years before ICF/IAF signature, will be coded using the Medical Dictionary for Regulatory Activities (MedDRA®). The version of the MedDRA will be indicated in the footnote of relevant tables based on the current version used in the clinical data.

A summary of medical and surgical history will be presented by MedDRA system (Version 18.0 or higher) and system organ class (SOC) and preferred term (PT). A similar summary will be generated for the currently active abnormalities only, by SOC and PT. Listing will be provided for the ITT population.

Prior cancer history will also be summarized and listed as collected in the “Prior Cancer History Question”, “Prior Cancer History” and “Prior Cancer History II” pages of eCRF.

8.1.4. Prior and Concomitant Medications/Procedures

Medications reported on the eCRF will be coded to therapeutic drug classes and generic drug names using Anatomical Therapeutic Chemical (ATC) coding scheme of the World Health Organization (WHO) drug dictionary (WHO-DDE March 2015 will be the initial version used, with subsequent eventual updates). Medications/procedures will be recorded from the time of the signing of informed consent/assent (medications within 14 days) until 28 days after the last dose of the IP. All prior medications/procedures related to AML or any malignancy, and received at any point in subjects history should be recorded on the CRF at screening, regardless of time.

Medications initiated prior to the start of study treatment and continued after the start of study treatment will be counted as both prior and concomitant medications. In the occurrence of partial dates, refer to Appendix 18.4 where the date imputation guideline is located.

A summary showing the number and percentage of subjects who took prior/concomitant medications will be presented by WHO therapeutic drug class and generic drug name. Therapeutic drug class and generic drug name will be listed in alphabetical order. A separate summary showing the number and percentage of subjects who underwent prior/concomitant procedures will be presented by MedDRA SOC and PT. SOC and PT will be listed in alphabetical order. Prior medication/procedure summaries will be presented for the ITT population while concomitant medication/procedure summaries will be presented for safety population.

A complete list of all prior and concomitant medications (prescription, over the counter, nutritional, fiber supplements, etc.), indication/diagnosis, dose, dosing regimen (frequency, route), and start and stop dates used prior to and during the study will be reported. A separate complete list of all prior and concomitant procedures, indication and date of procedure or surgery will be reported.

8.1.4.1. Prior Medications/Procedures

Prior medications and procedures are defined as medications and procedures starting before the start of the study treatment and either ending before the start of the study treatment or continuing after study treatment start. A summary showing the number and percentage of subjects who took prior medications will be presented for the ITT population.

Prior medications collected on the “Prior/Concomitant Medication” eCRF page and prior procedures collected on the “Prior/Concomitant procedures” eCRF page will be summarized.

Medications/procedures collected on the “Prior Radiation Therapies”, “Prior Cancer Surgeries for this Disease”, “Prior Hormonal Anti-Cancer Therapies for this Disease”, “Prior Systemic Anti-Cancer Therapies”, “Procedures for Prior Cancers Not Under Study”, and “Radiation Treatment For Prior Cancers Not Under Study” eCRF pages will be summarized for the safety population and listed for the ITT population.

8.1.4.2. Concomitant Medications/Procedures

Concomitant medications and procedures are defined as medications and procedures either initiated before the first dose of study drug and continuing during the study treatment, or initiated between first date of first dose of study drug and 28 days from the date of last dose of study medication.

Concomitant medications collected on the “Prior/Concomitant Medication” eCRF pages and concomitant procedures collected on the “Prior/Concomitant procedures” eCRF page will be summarized for the safety population.

A separate listing will be provided for data collected in the “Intrathecal Cytarabine” eCRF page and “Stem cell transplant” eCRF page for the ITT population.

9. STUDY TREATMENT AND EXTENT OF EXPOSURE

All study treatment and extent of exposure summaries will be provided based on the RR and safety populations. Descriptive statistics will be provided for treatment duration, average weekly dose, number of cycles, cumulative dose, dose intensity, relative dose intensity, treatment exposure and dose reductions / interruptions. Study drug record will be presented in a listing for the safety population.

The fixed Treatment Period and OEP treatment period will be considered together as a unique period for exposure analysis. In addition, summary statistics for treatment duration and dose information will be provided only for subjects that enter the OEP treatment phase and is limited to the OEP period.

9.1. Treatment Duration

Treatment Duration (weeks) is defined as:

$$[(\text{date of end of treatment}) - (\text{date of first treatment}) + 1] / 7$$

Date of first treatment is defined as the date of the first non-zero dose of lenalidomide administered for each phase, fixed phase and OEP phase.

Date of end of treatment is defined as follows:

- For subjects who completed 12 (or more if the subject entered the OEP of treatment) full cycles of lenalidomide, the end of lenalidomide is defined as Day 28 of last completed cycle 12.
- For subjects not considered in the previous point and for subjects who prematurely discontinued lenalidomide before day 21 of the cycle, the end of lenalidomide is the date either the investigator or subject decided to prematurely discontinue lenalidomide, which is referred to as “Date of Completion/Discontinuation” recorded on the eCRF page called “Disposition - Treatment” (or “Disposition - Treatment OEP” if the subject entered the OEP of treatment).

Descriptive statistics will be provided for treatment duration (n, Mean, StdDev, Median, Q1, Q3, Min, Max), total number of cycles completed (frequency count); if a subject has completed the 21 treatment days, the cycle will be considered completed. In addition, summary statistics will be provided only for subjects that enter the OEP treatment phase and limited to the OEP period.

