9.2. Cumulative Dose

Cumulative dose of lenalidomide will be computed as the sum of all doses administered, defined as the values entered on the actual dose assigned field on the dosing eCRF, taken across the treatment period (including OEP). Cumulative dose will be in mg/kg for all subjects.

Descriptive statistics will be presented for cumulative dose for subjects in the RR and safety population. Tabulations will be presented as dose information, by cycle and overall separately. In addition, for the OEP overall (ie all OEP cycles together) period, summary statistics will be provided for subjects that will enter the OEP treatment phase.

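### SAP 9.1, read literally, ends treatment duration at Cycle 12 for extension subjects while their cumulative dose runs on, inflating dose intensity by N/12 and leaving the extension-only figure undefined

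*SAP*

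**What the plan says.** SAP 9.1 computes treatment duration in weeks from a start date and an end date, and gives two end-date rules.

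- The first applies "For subjects who completed 12 (or more if the subject entered the OEP of treatment) full cycles of lenalidomide", so extension subjects are named. For this group "the end of lenalidomide is defined as Day 28 of last completed cycle 12".
- The second applies "For subjects not considered in the previous point and for subjects who prematurely discontinued lenalidomide before day 21 of the cycle". It uses the completion or discontinuation date on the treatment disposition page, "or “Disposition - Treatment OEP” if the subject entered the OEP of treatment".

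The start date is set separately by phase: "Date of first treatment is defined as the date of the first non-zero dose of lenalidomide administered for each phase, fixed phase and OEP phase".

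The surrounding sections treat the two phases as one. SAP 9 says "The fixed Treatment Period and OEP treatment period will be considered together as a unique period for exposure analysis", and adds an OEP-only summary for those who enter it. SAP 9.2 sums all doses "taken across the treatment period (including OEP"). SAP 9.5 divides that sum by treatment duration, and SAP 9.6 divides the result by a planned 14 mg/kg/week.

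SAP 5.2 has its own treatment end date: the discontinuation date for subjects who stopped before the cutoff, and 27 days after the first dose of the last cycle for those still on treatment. SAP 16, which lists changed and dropped analyses, does not touch the exposure definitions.

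**The concern.** For an extension subject under the first rule, the numerator of dose intensity covers both phases and the denominator stops at the end of Cycle 12. The longer the subject stays in the extension, the larger the reported dose intensity, whatever was actually taken. The subjects affected are the longest treated.

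The same end date falls before the OEP start date defined in the same section, so the OEP-only duration and dose intensity that the SAP asks for cannot be computed sensibly. In addition, an extension subject who stops early in a cycle satisfies both rules, which can give end dates many weeks apart.

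**Working it through.** **Inputs**

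- Dose 2 mg/kg/day (maximum 70 mg/day) on 21 of 28 days: SAP 4.1, protocol 8.2.
- Duration = (end − start + 1)/7 weeks: SAP 9.1.
- Dose intensity = cumulative dose/duration: SAP 9.5.
- Planned weekly dose 14 mg/kg/week: SAP 9.6.
- Total cycles N: an assumption. Protocol Appendix L sets no maximum for the OEP, and the documents do not say how many subjects entered it.

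**1. The SAP's own figure.** 2 × 7 = 14 mg/kg/week, which reproduces as a dosing week. Averaged over a 28-day cycle, full dosing is 2 × 21/4 = 10.5 mg/kg/week, so a fully dosed subject has relative dose intensity 10.5/14 = 75%. That 14 ignores the rest week is a separate matter; it serves here only as the SAP's benchmark.

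**2. Pooled dose intensity under the first rule.** With undelayed cycles, Cycle 12 Day 28 is study day 12 × 28 = 336, or 48 weeks. Cumulative dose is 42N mg/kg and actual duration is 4N weeks.

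- As written: 42N/48.
- Over the actual duration: 42N/4N = 10.5.
- Ratio: 4N/48 = N/12.

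| N (assumed) | Cumulative dose, mg/kg | Dose intensity as written | Ratio to 10.5 | Relative dose intensity as written (against 75%) |
|---|---|---|---|---|
| 12 | 504 | 10.5 | 1.00 | 75% |
| 13 | 546 | 11.375 | 1.08 | 81.25% |
| 15 | 630 | 13.125 | 1.25 | 93.75% |
| 18 | 756 | 15.75 | 1.50 | 112.5% |
| 24 | 1008 | 21.0 | 2.00 | 150% |

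A single extension cycle moves a fully dosed subject from the 70 to <80% band of SAP 9.6 into the 80 to <90% band.

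**3. Dose level.** The factor does not depend on dose. With 12 cycles at 2 mg/kg and 6 at 1 mg/kg, cumulative dose is 504 + 126 = 630; 630/48 = 13.125 against 630/72 = 8.75, again 1.5.

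**4. Delays.** SAP 9.7 allows a cycle to start up to 14 days late. For 18 cycles:

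- Delays only before Cycles 14 to 18: Cycle 18 Day 28 falls on day 336 + 5 × 42 + 28 = 574, and 574/336 = 1.71.
- Each of Cycles 1 to 12 occupying 42 days, with no later delay: Cycle 12 Day 28 falls on 11 × 42 + 28 = 490 and Cycle 18 Day 28 on 12 × 42 + 5 × 28 + 28 = 672; 672/490 = 1.37.

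So N/12 (here 1.5) is exact for undelayed cycles but is not a ceiling.

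**5. OEP-only duration.** If the OEP starts the day after Cycle 12 ends, the formula gives (336 − 337 + 1)/7 = 0 weeks, and dose intensity divides by zero.

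**6. Overlap of the two rules.** Take a fully dosed subject who stops on Day 10 of Cycle 18, with that day as the disposition date. Dose is 2 × (17 × 21 + 10) = 734 mg/kg.

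- Second rule: (17 × 28 + 10)/7 = 69.43 weeks; 734/69.43 = 10.57 mg/kg/week, with no inflation.
- First rule: 734/48 = 15.29 mg/kg/week.

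If the second rule prevails, this subject has 69.4 weeks, while one who completes Cycle 18 has 48 weeks and 15.75 mg/kg/week: more dosing, shorter recorded duration.

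**7. What is not affected.** Average weekly dose (SAP 9.4) divides by days on drug, so the end-date rule does not enter it.

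**The case against.** The strongest reply is that the 12 is a leftover from editing. The rule expressly covers more than 12 cycles, speaks of the last completed cycle (pointless if that is always Cycle 12), and sits in a section that pools the phases and requires an OEP-only duration that the literal text makes impossible. A programmer may well read it as the last completed cycle. This stands, and it means the inflation is conditional on literal programming. It does not remove the need for correction, because the SAP exists to fix such rules before analysis.

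Two stronger readings are tempting.

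- A reader might infer that dose intensity is overstated for every extension subject. The documents do not support that: those who stop before Day 21 of a cycle also meet the second rule, which uses the OEP disposition date.
- A reader might also infer an error for subjects who take all 21 doses and stop before Day 28, since SAP 9.1 says "if a subject has completed the 21 treatment days, the cycle will be considered completed" yet ends their duration on the disposition date. Stopping on Day 22 gives 42/(22/7) = 13.4 against 42/4 = 10.5 mg/kg/week, a gap that closes by Day 28. But that sentence governs the count of completed cycles, and ending duration at the recorded discontinuation date is a defined rule that SAP 5.2 also uses. Whether the rest week counts after a permanent stop is a convention.

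The consequences are also limited. Exposure summaries are descriptive, and the Stage 1 and final decisions rest on CR/CRi counts.

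**Conclusion.** The point holds as a conditional one. SAP 9.1 is internally inconsistent. Programmed as written, it inflates pooled dose intensity and relative dose intensity by N/12 for extension subjects under the first rule, and makes OEP-only dose intensity undefined.

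The sizes rest on assumed cycle totals, full uncapped dosing and undelayed cycles; the ratio itself needs only the last of these. The effect on summary tables depends on how many subjects entered the OEP and for how long, which the documents do not say. No efficacy conclusion is affected. This is a minor correction to a derivation rule.

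**What to change.** In SAP 9.1:

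- Delete the 12, and define the end date as Day 28 of the last completed cycle of the phase being analysed (fixed, OEP or pooled), capped at death or data cutoff.
- State that the second rule takes precedence when the last cycle started was not completed.
- State which convention applies to a subject who finishes the 21 dosing days and stops before Day 28.

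Align the treatment end date in SAP 5.2 with this, including for subjects still on treatment at the cutoff, so that one rule serves both sections.

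The cost is a few sentences of SAP text and a small change to the derivation program. No new data are needed.

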9.2. Cumulative Dose

Cumulative dose of lenalidomide will be computed as the sum of all doses administered, defined as the values entered on the actual dose assigned field on the dosing eCRF, taken across the treatment period (including OEP). Cumulative dose will be in mg/kg for all subjects.

Descriptive statistics will be presented for cumulative dose for subjects in the RR and safety population. Tabulations will be presented as dose information, by cycle and overall separately. In addition, for the OEP overall (ie all OEP cycles together) period, summary statistics will be provided for subjects that will enter the OEP treatment phase.

9.3. Dose Exposure

Dose exposure in weeks is defined as the total number of actual days on drug during the treatment period divided by 7. Descriptive statistics will be presented for dose exposure for subjects in the RR and safety population. Tabulations will be presented as dose information, by cycle and overall separately. In addition, for the OEP overall period, summary statistics will be provided for subjects that will enter the OEP treatment phase.

9.4. Average Weekly Dose

Average weekly dose will be calculated as the cumulative dose in mg/kg divided by dose exposure in weeks. Descriptive statistics will be presented for average weekly dose for subjects in the RR and safety population. Tabulations will be presented as dose information, by cycle and overall separately. In addition, for the OEP overall period, summary statistics will be provided for subjects that will enter the OEP treatment phase.

9.5. Dose Intensity

Dose intensity during the treatment is defined as the cumulative dose in mg/kg divided by the treatment duration in weeks.

Dose intensities will be calculated as follows: Dose intensity (mg/kg/weeks) = [cumulative dose for lenalidomide in mg/kg]/[treatment duration in weeks].

Dose intensity will be presented as dose information, by cycle and overall separately, for the treatment period of the study for the response rate and safety populations. In addition, for the OEP overall period, summary statistics will be provided for subjects that will enter the OEP treatment phase.

9.6. Relative Dose Intensity

Relative dose intensity is the dose intensity divided by the protocol specified weekly dose (both expressed as mg/m²/week), expressed as a percentage:

$$\text{Relative dose intensity (\%)} = (\text{dose intensity} / \text{protocol weekly dose}) * 100\%$$

where protocol weekly dose (the planned dose intensity) is the mean of the expected weekly doses (14 mg/kg/week) of all cycles of treatment initiated by the subject.

Relative dose intensity of lenalidomide will be categorized into <70%, ≥70% to < 80%, and ≥80 to <90% and ≥90%, and frequency counts will be provided together with summary statistics for the RR and safety population and will be tabulated together with overall dose information. In addition, summary statistics will be provided only for subjects that enter the OEP treatment phase and limited to the OEP period.

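### SAP 9.6 sets planned dose intensity at 14 mg/kg/week, but its numerator counts rest weeks, so a fully compliant uncapped subject on full cycles scores 75%

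*SAP*

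**What the plan says.** The definitions run through SAP Section 9.

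- **9.1, duration.** Treatment duration is calendar time: end date minus first-dose date plus one, divided by 7. It starts on "the date of the first non-zero dose of lenalidomide administered for each phase, fixed phase and OEP phase". For subjects who complete 12 or more cycles, "the end of lenalidomide is defined as Day 28 of last completed cycle 12". Otherwise it ends on the completion or discontinuation date in the disposition record.
- **9.2, cumulative dose.** This is the sum of "the values entered on the actual dose assigned field on the dosing eCRF", reported in mg/kg.
- **9.3 and 9.4, days-on-drug measures.** "Dose exposure in weeks is defined as the total number of actual days on drug during the treatment period divided by 7". "Average weekly dose will be calculated as the cumulative dose in mg/kg divided by dose exposure in weeks".
- **9.5, dose intensity.** "Dose intensity during the treatment is defined as the cumulative dose in mg/kg divided by the treatment duration in weeks".
- **9.6, RDI.** Dose intensity is "divided by the protocol specified weekly dose (both expressed as mg/m²/week"), where "protocol weekly dose (the planned dose intensity) is the mean of the expected weekly doses (14 mg/kg/week) of all cycles of treatment" started by the subject. Results are counted in four bands: below 70%, 70 to below 80%, 80 to below 90%, and 90% or more, for the RR and safety populations.

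SAP 4.1 gives the schedule: 2 mg/kg/day, at most 70 mg/day, on the first 21 days of each 28-day cycle. SAP 5.2 has a separate end-date rule: for a subject still on treatment at the clinical cutoff, treatment ends on the 28th day of the current cycle.

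**The concern.** The two halves of the RDI ratio use different clocks. The denominator is a week with drug on all seven days. The numerator is averaged over calendar weeks, one in four of which has no scheduled drug. A subject who follows the protocol exactly is then shown as under-dosed.

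The banded table is what a reader will use to judge whether children received the intended dose, and the trial's conclusion is worded in terms of the dose level tested. As defined, the table would show under-dosing that did not occur. It would also make subjects who stop in Cycle 1 look better dosed than those who stay on treatment for months.

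**Working it through.** **Inputs.** 2 mg/kg/day, 70 mg/day cap, 21 of 28 days (SAP 4.1); calendar duration (9.1); dose intensity (9.5); planned value 14 mg/kg/week (9.6); cutoff rule (5.2); dose-rounding tables (Protocol Appendices B and C).

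**1. The plan's figure.** 2 x 7 = 14 mg/kg/week. It is also what the days-on-drug measure in 9.4 returns for a compliant uncapped subject: 42 mg/kg / (21/7 weeks) = 14. The multiplication is right; the basis does not match 9.5.

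**2. Planned value on the 9.5 basis.** 2 x 21 / (28/7) = 42/4 = 10.5 mg/kg/week. The result is the same over 1 cycle (42/4), 4 cycles (168/16) and 12 cycles (504/48).

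**3. RDI as printed, full cycles, uncapped.** 10.5/14 = 75.0%, in the 70 to below 80% band.

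**4. Compliant uncapped subjects who have stopped.** RDI reduces to scheduled dosing days divided by calendar days.

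| Stop | Ratio | RDI |
|---|---|---|
| Up to Cycle 1 Day 21 | e.g. 21/21 | 100% |
| Cycle 1 Day 22 | 21/22 | 95.5% |
| Cycle 1 Day 23 | 21/23 | 91.3% |
| Cycle 1 Day 24 | 21/24 | 87.5% |
| Cycle 2 Day 21 | 42/49 | 85.7% |
| Cycle 4 Day 21 | 84/105 | 80.0% |
| Cycle 4 Day 22 | 84/106 | 79.2% |
| Day 28 of any cycle | 21/28 | 75.0% |

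Over stop days 1 to 336 the range is 75% to 100%. The 90% band is reached only by a stop on or before Day 23, and 80% is not reached after Day 105.

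**5. Subjects still on treatment at cutoff.** If the 5.2 end date is used, days not yet reached count in the duration. Example, cutoff on Cycle 5 Day 5: dose 2 x (84 + 5) = 178 mg/kg; duration 140/7 = 20 weeks; 178/20 = 8.9; 8.9/14 = 63.6%.

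**6. Effects that depend on 9.2.** Suppose the mg/kg dose means administered mg divided by body weight, with the weight used for dosing. Then on full cycles:
- *Rounding, capsules.* A calculated dose just under 22.5 mg is rounded to 22 and given as 20 mg: 75 x 20/22.5 = 66.7% (a limit). At 18.5 mg, rounded to 19 and given as 20 mg: 75 x 20/18.5 = 81.1%.
- *Rounding, suspension.* Just under 16.5 mg, given as 16 mg: 75 x 16/16.5 = 72.7%. At 14.5 mg, rounded to 15 and given as 16 mg: 75 x 16/14.5 = 82.8%.
- *Cap.* Above 35 kg the score is 75% x 35/weight; at an assumed 40 kg, 65.6%.

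If the field holds the mg/kg dose level instead, none of these effects arises.

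**The case against.** **The word mean may imply averaging over weeks.** Averaging a constant 14 is redundant, so the authors may have meant 14, 14, 14 and 0 over the four weeks of a cycle, which gives 10.5. That may well be the intent. But the text averages over cycles, prints only 14, and names it the planned dose intensity; a programmer following it divides by 14. On the averaging reading the printed number still needs correcting, and so does the unit label.

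**It is one descriptive table.** This stands. RDI enters no decision rule. Dose intensity in mg/kg/week, cumulative dose, average weekly dose, and reductions and interruptions are all tabulated separately, so a reader can divide dose intensity by 10.5 for uncapped full-cycle subjects. This limits the consequence but does not make the banded table correct.

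**Replacing 14 by 10.5 would be enough.** It would be for full cycles. A compliant uncapped subject who stops by Cycle 1 Day 21 would then score 14/10.5 = 133%, so the constant alone does not solve the mismatch.

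**The rounding figures look more precise than they are.** This also stands: they are conditional on an unstated conversion, and the extremes are limits. The 82.8% end needs a weight of 14.5/2 = 7.25 kg.

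**Conclusion.** The definition is wrong as written. For a subject who takes every scheduled dose at the starting dose, below the cap and over full 28-day cycles, the printed RDI is 75% where 100% is meant, and the band of 90% or more is out of reach. For compliant uncapped subjects who have stopped, the score runs from 100% down to 75% and depends only on the stopping day. For those on treatment at cutoff it can be lower, if the 5.2 end date is applied. These figures are before dose-table rounding. Rounding (limits 66.7% to 82.8% on full cycles) and the 70 mg cap alter the score only if 9.2 means administered mg over body weight, which the SAP does not say. The mg/m²/week label is a separate error that does not change the 75%.

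A reader might infer that every compliant subject scores 75%, that the activity conclusion is compromised, or that the trial's dosing is in question. The documents support none of these. The score varies with stopping day. The primary endpoint and both Simon thresholds count CR/CRi responses and do not use RDI. The fault lies in an analysis definition, not in a dosing rule.

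**What to change.** Put both halves of the ratio on the same time base in SAP 9.6:

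- RDI = actual cumulative dose / planned cumulative dose. Planned cumulative dose = protocol starting daily dose in mg/kg (with the 70 mg/day cap applied) x scheduled dosing days.
- Scheduled dosing days are Days 1 to 21 of each 28-day cycle, counted from the first dose of the period summarised up to the earlier of treatment end and data cutoff. For uncapped full cycles this equals 10.5 mg/kg/week.
- For subjects on treatment at cutoff, state that this end point replaces the 5.2 end date for RDI. The Cycle 5 Day 5 example becomes 178/178 = 100%.
- State that the OEP-only table counts from the first OEP dose and uses the protocol starting dose as its reference. Subjects who enter the OEP on a reduced dose will then score below 100% by construction.
- Replace mg/m²/week with mg/kg/week.
- In 9.2, state how the eCRF dose is converted to mg/kg, including which weight is used.

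One downside should be stated. A cycle-start delay of up to 7 days can leave the ratio at 100%. With a 7-day delay before Cycle 2, a stop on Day 56 gives 42/42 = 100% and a stop on Day 70 gives 49/56 = 87.5%. Delays should therefore be read from the 9.7 summary, which already counts them with interruptions.

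The cost is one formula with its end-date and OEP notes, one unit label, one line in 9.2 and the related programming. No new data are collected and no dosing rule is changed.
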